### 7. Product Description

#### 7.1. General

The device under study is the Emprint™ Ablation Catheter Kit with Thermosphere™ Technology (CA108L1), an endoscopic ablation accessory for use with the Emprint™ Ablation System. The Emprint™ Ablation Catheter Kit with Thermosphere™ Technology is for use with the Emprint™ Ablation System with Thermosphere™ Technology for the ablation of lung tissue.

Microwave-based soft tissue ablation uses microwave energy to increase target tissue temperature resulting in thermocoagulation and cellular death. Microwave energy is supplied by a generator and emits from the exposed portion of an antenna. The Evident™ Microwave Ablation System was designed to provide microwave power for ablation of soft tissue during medical procedures. It received the CE mark in 2007 and 510k clearance in 2008. The Emprint™ Ablation System is an evolution of the technology within the Evident™ Microwave Ablation System, which received both CE mark and 510k clearance in 2014. The Emprint™ system utilizes higher power, a more efficient cable and antenna design, and an antenna designed to create a more spherical field pattern (Thermosphere™ technology). An ablation catheter has been added as an accessory to the Emprint™ system- to be used in a bronchoscopic approach for lung ablation.

MDT18010ILSBA

Version 4.0

26-SEP-2019

Page 18 of 50

The shelf life of the product is intended to be expanded to 24 months which may occur during the course of the study. No other changes to the product are anticipated.

#### 7.2. Dosage Form and Route of Administration

The Emprint™ Ablation Catheter Kit with Thermosphere™ Technology is deployed endoscopically (bronchoscopically) and will be used to conduct bronchoscopic ablations in the lung using the superDimension™ navigation system.

#### 7.3. Manufacturer

The Emprint™ Ablation Catheter Kit with Thermosphere™ Technology is manufactured by Covidien Ilc, an indirect wholly owned subsidiary of Medtronic plc.

## 7.4. Packaging

The Emprint™ Ablation Catheter will be provided to health care providers as part of a kit (Catalog No. CA108L1). In addition to the catheter, the kit includes a stabilizing rail that is attached to the Edge Bronchoscope Adapter and a locking clip. Products used in this study that are commercially available are packaged and labelled accordingly. Labeling of devices will be provided in accordance with local language requirements.

[figure not shown]
MDT18010ILSBA

Version 4.0

26-SEP-2019

Page 19 of 50

**Figure 1. The Emprint™ Ablation Catheter, rail, and clip.** (1) Intravenous IV Bag Spike; (2) Drip Chamber; (3) Pump Tubing; (4) Generator Connector; (5) Ablation Catheter Handle; (6) Top Groove, (7) Control Ring, (8) Radiating Section; (9) Clip; (10) Rail

# 7.5. Intended Use and Population

The Emprint™ Ablation System with Thermosphere™ Technology is intended for use in percutaneous, laparoscopic, endoscopic, and intraoperative coagulation (ablation) of soft tissue, including partial or complete ablation of non-resectable liver tumors.

The Emprint™ Ablation System with Thermosphere™ Technology is not intended for use in cardiac procedures.

This study will evaluate the population of patients where the use of the Emprint™ Ablation Catheter Kit with Thermosphere™ Technology is conducted via a bronchoscope for ablation of malignant nodules in the lung.

# 7.6. Equipment

The Emprint™ Ablation Catheter is designed for use with the Emprint™ system components (Figure 1 above) and is compatible with the Covidien Edge™ or Edge™ Firm Tip Extended Working Channel (EWC)

MDT18010ILSBA

Version 4.0

26-SEP-2019

Page 20 of 50

and Edge Bronchoscope Adapter. The system's reusable cable (connects the percutaneous antenna to the microwave generator) is not used with the flexible catheter, as the catheter is designed to connect to the generator directly.

Sites must have access to the superDimension™ navigation system utilizing either software version 6 or higher at the time of study initiation for each site, with potential for upgrade to the most recent software release throughout the duration of the study. Sites must also have a procedure room equipped with a cone-beam computed tomography (CBCT) imaging system. Sites may also use the CrossCountry™ Transbronchial Access Tool to obtain access.

#### 7.7. Product Use

For the purpose of this post-market clinical study, the Emprint™ ablation catheter and Emprint™ Ablation Catheter Kit with Thermosphere™ Technology should be used according to manufacturer's Instructions for Use and standard-of-care. Typically, one ablation catheter is used per procedure but more than one may be used at the investigator's discretion.

#### 7.8. Product Training Requirements

Physicians must have documented completion of the manufacturer's bronchoscopic ablation training program and sufficient experience conducting ENB procedures and in using CBCT, the CrossCountry™ Access Tool, and the Emprint™ ablation system. Documented completion will be recorded on the Study Enrollment Eligibility Form.

# 7.9. Product Receipt, Tracking, Storage, Return, and Accountability

The study devices provided by the Sponsor will be recorded on the study specific Product Accountability Log. Information to be recorded will include, but is not limited to, date of receipt, and the date used or date of return to the Sponsor. The study-specific devices shall be kept in a locked room.

The study devices provided by the Sponsor will be labeled with a study-specific label indicating that it is only to be used for study subjects.

#### 7.10. Intended Claims

The purpose of this investigation is to characterize the safety and performance of the Emprint™ Ablation Catheter Kit with Thermosphere™ Technology in clinical use. This study does not specifically evaluate efficacy claims.

MDT18010ILSBA

Version 4.0

26-SEP-2019

Page 21 of 50

## 8. Selection of Subjects

#### 8.1. Study Population

The study population will consist of consented adults undergoing bronchoscopic lung ablation procedures using electromagnetic navigation bronchoscopy (ENB). Additional inclusion and exclusion criteria are listed below.

## 8.2. Subject Enrollment

Up to 30 subjects will be enrolled at up to 3 sites in up to 3 regions. The minimum and maximum number of subjects to be included at each site are not prespecified since the study is not statistically powered.

For the purpose of this clinical study investigational plan, the point of enrollment is defined as the insertion of the Emprint™ Ablation Catheter Kit with Thermosphere™ Technology into the EWC.

Subjects will be approached to obtain written informed consent prior to any institution non-standard-of-care assessments or study-specific data being collected. During the index procedure imaging, nodule eligibility criteria will be re-confirmed. Any patients with nodules no longer meeting eligibility criteria will not be enrolled. Subjects who provide study consent but then are determined to be ineligible prior to the insertion of the ablation catheter will be considered screen failures and documented as such in the database.

#### 8.3. Inclusion Criteria

- 1. Subject is ≥ 18 years of age
- 2. Subject has provided informed consent
- 3. Subject is able and willing to comply with the study follow-up schedule
- 4. Subject has a definitive diagnosis of cancer in the lung
- 5. Target nodule is ≤ 30mm in maximum diameter
- 6. There is ≥ 5mm of nodule-free lung parenchyma between target nodule and pleura or fissure
- 7. Subject is a candidate for an elective ENB procedure
- 8. Subject is a candidate for an elective lung ablation procedure according to standard of care and product Instructions for Use
- 9. Subject is not a candidate for lung surgery or refuses lung surgery
- 10. Subject is not a candidate for stereotactic body radiation therapy (SBRT) or refuses SBRT

MDT18010ILSBA

Version 4.0

26-SEP-2019

Page 22 of 50

#### 8.4. Exclusion Criteria

- 1. Target nodule is abutting main stem bronchus, main pulmonary vasculature, esophagus and/or trachea
- 2. Patients currently diagnosed with Global Initiative for Chronic Obstructive Lung Disease (GOLD) Stage IV emphysema
- 3. Female subjects who are pregnant or nursing as determined by standard site practices
- 4. Subject has participated in an investigational drug or device research study within 30 days of enrollment that would interfere with this study
- 5. The investigator determines that participation in the study may jeopardize the safety or welfare of the subject

### 9. Study Procedures

Following confirmation of eligibility and informed consent, subjects with inoperable lung nodules will undergo an ablation procedure using a bronchoscopic approach. A target nodule will be identified on a pre-procedure CBCT scan. Nodule localization will be aided by ENB using the superDimension™ navigation system. Once localized, if no suitable bronchus sign leads to the proposed area to ablate, access to the region may be obtained using the CrossCountry™ Transbronchial Access Tool. Once ablation region access has been achieved, the ablation catheter will be placed inside the EWC and will be unsheathed inside the target nodule. Correct positioning will be verified using CBCT and the nodule will then be ablated. AEs related to Emprint™ Ablation Catheter Kit with Thermosphere™ Technology, accessory devices, or study procedures will be captured and reported until the 1-month follow-up visit.

#### 9.1. Schedule of Events

Variables to be collected (following confirmation of eligibility and written informed consent), follow-up visit schedule, and tests to be performed at each visit are described in **Table 1** below.

MDT18010ILSBA Version 4.0 26-SEP-2019

Page 23 of 50

Table 1. Schedule of Events.

	Baseline (Day -30 to Day 0)	During the Procedure and Immediately Post- Procedure	1-Month Follow-up (20 to 40 Days Post- Procedure)
Subject demographics	Х		
Medical history (Lung Diagnoses, Previous Lung procedures, Lung function tests, etc.)	Х		
Eligibility assessment	Х	Х	
Nodule characteristics		Х	
Procedural information		Х	
Adverse event assessment		Х	Х
Imaging	X*	Х	Х
Concomitant medications	Х	Х	Х
Quality of life survey (EQ-5D)	Х		Х
Bronchoscopic Ablation Patient Pain and Satisfaction Survey			Х

\*Standard-of-care CT scan performed prior to consent.

# 9.2. Subject Screening

A baseline visit will be performed within 30 days prior to the scheduled procedure to assess study eligibility. During the index procedure imaging, nodule eligibility criteria will be re-confirmed. Consented subjects will be considered for the study if they meet specified inclusion criteria and none of the exclusion criteria. The criteria for enrollment must be followed explicitly.

Subjects who provide study consent, but then are determined to be ineligible prior to the start of the ablation portion of the procedure will be considered screen failures and will not require additional study follow-up visits. The reason for the Screen Failure will be clearly documented on the applicable electronic case report forms (eCRFs). Screen failures will not be counted towards the number of study subjects.

MDT18010ILSBA

Version 4.0

26-SEP-2019

Page 24 of 50

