7.1.2 Analysis Sets

The point of enrollment is defined as the insertion of the EmprintTM Ablation Catheter Kit with ThermosphereTM Technology into the EWC. Unless otherwise specified, analysis of reported outcomes will include all available data for all enrolled subjects.

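### Protocol 9.2 sets an undefined, possibly later screen-failure cut-off than 8.2 and 14.1, so a subject found ineligible after catheter insertion could miss the 1-month safety visit and be counted inconsistently

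*Protocol*

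**What the plan says.** Protocol 8.2 fixes enrolment at a physical event: "the point of enrollment is defined as the insertion of the Emprint™ Ablation Catheter Kit with Thermosphere™ Technology into the EWC". Sections 9.8.4, 11.1 and 14.1 and SAP 7.1.1 and 7.1.2 repeat this definition. Section 11.1 also starts AE collection there.

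Sections 8.2 and 14.1 tie screen failure to the same event: a consented subject "determined to be ineligible prior to the insertion of the ablation catheter will be considered screen failures".

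Section 9.2 uses a different boundary. A consented subject found "ineligible prior to the start of the ablation portion of the procedure will be considered screen failures and will not require additional study follow-up". It adds: "Screen failures will not be counted towards the number of study subjects".

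Section 9 gives the order of steps. The catheter goes into the extended working channel (EWC) and is unsheathed in the nodule. Then: "Correct positioning will be verified using CBCT and the nodule will then be ablated".

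SAP 7.1.2 states that "analysis of reported outcomes will include all available data for all enrolled subjects", unless otherwise specified.

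**The concern.** Both cut-offs are current text, and they agree only if the ablation part of the procedure starts at catheter insertion. The protocol does not say that it does. If that part starts with energy delivery, there is an interval in which the study device is already in the lung, the subject is enrolled and AE collection is running, yet 9.2 still allows screen-failure status.

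The primary endpoint is the rate of AEs related to the catheter kit through 1 month. A subject in this interval has been exposed to the catheter and is at risk of that endpoint. Section 9.2 waives the visit at which later events would be found. The SAP has no rule for a subject who was inserted and then recorded as a screen failure, so the count may depend on which section the site or the programmer follows.

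**Working it through.** **No planned figure to reproduce.** The sample size does not rest on a power calculation (SAP 6). The protocol synopsis gives a maximum of 30 subjects and an approximate minimum of 20. The main check is therefore of the text.

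**Step 1. The same subject under each rule** (inserted, then found ineligible before energy is applied):

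| | 8.2, 11.1, 14.1, SAP 7.1.2 | 9.2, if its boundary is energy delivery |
|---|---|---|
| Status | Enrolled | Screen failure |
| AE collection | From insertion | Not addressed |
| 1-month visit | Scheduled (Table 1) | Not required |
| Counted as a study subject | Yes | No |

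**Step 2. Can the case arise?** Section 9 puts unsheathing and a cone-beam CT check between insertion and ablation. Sections 8.2, 9.2 and 9.8.4 place the nodule eligibility re-check during index procedure imaging, without stating that this imaging must be finished before insertion. Table 1 marks eligibility assessment in the column for the procedure and the period immediately after it. A failed criterion, such as the 5 mm distance to pleura or fissure, could come to light after insertion.

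**Step 3. Which denominators keep the subject?**
- Primary and secondary safety rates (SAP 7.7): N is everyone with an ENB index procedure. The subject is kept.
- Technical success (SAP 7.7.2.6): N is everyone enrolled. The subject is kept.
- Technique efficacy (SAP 7.7.2.7): N is subjects with follow-up imaging. A subject excused from follow-up drops out, as does anyone not imaged.

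Keeping the subject in N does not recover an event that nobody looked for, and SAP 7.3 plans no imputation.

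**Step 4. Size.** The documents do not give the number k of such subjects; k = 1 to 3 is assumed. Intervals are two-sided 95% exact binomial, as in SAP 7.7. The lower limit is the 0.025 quantile of Beta(x, n − x + 1), and 0 when x = 0. The upper limit is the 0.975 quantile of Beta(x + 1, n − x), which for x = 0 equals 1 − 0.025^(1/n).

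Primary endpoint, k = 1, when this subject has the only related AE:

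| Handling | N = 30 | N = 20 |
|---|---|---|
| Kept and followed | 1/30 = 3.3% (0.1–17.2) | 1/20 = 5.0% (0.1–24.9) |
| Recorded as screen failure | 0/29 = 0% (0–11.9) | 0/19 = 0% (0–17.6) |
| Kept in N, late event missed | 0/30 = 0% (0–11.6) | 0/20 = 0% (0–16.8) |

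The last row uses 1 − 0.025^(1/30) = 0.116 and 1 − 0.025^(1/20) = 0.168.

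Other cases:
- k = 1, this subject event-free, two others with events: 2/30 = 6.7% (0.8–22.1) kept, 2/29 = 6.9% (0.8–22.8) dropped.
- k = 3, all three with events, plus two others: 5/30 = 16.7% (5.6–34.7) kept, 2/27 = 7.4% (0.9–24.3) dropped.
- Technical success if every ablated subject succeeds, N = 30: 29/30 = 96.7% against 29/29 = 100% (k = 1); 27/30 = 90.0% against 27/27 = 100% (k = 3).

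**The case against.** The strongest reply is that one loosely worded sentence should not override an enrolment definition repeated throughout both documents. A reader might infer from 9.2 that these subjects vanish from every rate. The SAP does not support that: read literally, its safety and technical-success denominators keep them. This part of the reply stands.

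Three further points have force:
- Section 9.2 covers only subjects found ineligible. Someone inserted but left unablated for technical reasons or comorbidity stays enrolled and counts against technical success, so the point does not extend to all non-ablated subjects.
- The ablation part could be meant in contrast to the navigation part; SAP 7.7.2.2 asks separately about relatedness to the ENB procedure and to the ablation procedure. On that reading the cut-offs coincide. The workflow figure that might settle this is not reproduced in the text available here.
- Sections 8.2 and 9.8.4 say that patients whose nodules fail the re-check are not enrolled, which implies a re-check before insertion. The later cone-beam CT has the stated purpose of checking position.

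A reader might also suspect that sites could pick the rule after seeing how insertion went. The documents do not support that charge: reasons for screen failure must be recorded, eligibility is fully source-verified (15.1), and AE collection begins at insertion.

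These points make the case less frequent and its effect smaller. They do not define the boundary in 9.2, restore a waived visit, or tell the analyst how to treat an inserted subject coded as a screen failure.

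**Conclusion.** Section 9.2 needs to be reconciled with 8.2 and 14.1. The conflict exists if the boundary in 9.2 is energy delivery, which the text permits but does not state. On that reading, a catheter-exposed, enrolled subject can be excused from the visit that ascertains the primary safety endpoint, and the documents disagree on whether the subject counts.

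The number affected is unknown and probably small. In a single-arm study of 20 to 30 subjects, one such subject with the only related event decides whether the primary rate is 3.3% or 5.0%, or zero. That is a chosen worst case. It would be wrong to infer that 9.2 always lowers AE rates, because dropping an event-free subject raises them slightly. Technical success is different: removing a non-ablated subject can only raise it or leave it unchanged.

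**What to change.** 1. In Protocol 9.2, replace the cut-off with the one in 8.2 and 14.1, so that screen failure is possible only before the ablation catheter enters the EWC. If the sponsor always meant this, the change is editorial.
2. State in the protocol and the SAP that every subject with catheter insertion is enrolled, including one found ineligible afterwards. If no ablation follows, the subject keeps the 1-month AE assessment already in Table 1, stays in the safety and technical-success denominators, and counts as not a technical success.
3. Describe the safety N in SAP 7.7 in the same terms as the analysis set in SAP 7.1.2.
4. Add a disposition row for subjects inserted but not ablated, with the reason.

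The cost is a few sentences and one table row. Technical success may look slightly lower, and a few non-ablated subjects will need the 1-month contact. Only study status, follow-up and counting change.

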#### 9.3. Prior and Concomitant Medications

All prior and concomitant medications should be managed according to standard-of-care.

### 9.4. Subject Consent

Subjects will be approached to obtain written informed consent prior to any institution non-standard-of-care assessments or study-specific data being collected. The purpose of the study and the benefits and risks of participating in the study will be explained to the subject and the consent process must be documented accordingly.

Subjects will be informed that their participation in this study is voluntary and that they may refuse to participate or discontinue from the study at any time. Additionally, subjects will be informed that despite signing informed consent, the screening assessments may demonstrate the subject is not a suitable candidate for the study or the ablation procedure and may be withdrawn. Subjects will be given the opportunity to ask the investigator questions so that they are adequately informed about the research.

After being informed of the nature of the study, subjects who agree to study participation must sign a written informed consent form (ICF) that has been approved by the appropriate Ethics Committee (EC) or Institutional Review Board (IRB) and Regulatory Authority if required per country, of the respective clinical site. A copy of the signed ICF must be provided to the subject.

For this study, the subject must sign and date the ICF personally. The use of Legally Authorized Representatives, Healthcare Proxies or any other means of representation will not be permitted. All procedures evaluated in this study are considered elective; no emergency procedures or circumstances where the subject is unable to give consent will be permitted according to the study inclusion criteria.

If new information becomes available that may affect a subject's decision to continue to take part in the study, this information will be discussed with the subject.

The principal investigator or his/her authorized designee must conduct the informed consent process.

# 9.5. Randomization and Treatment Assignment

Not applicable. There are no treatment arms or randomizations required for this study.

# 9.6. Medication Compliance

Not applicable. There are no required medications or medication protocols for this study.

MDT18010ILSBA

Version 4.0

26-SEP-2019

Page 25 of 50

# 9.7. Assessment of Efficacy

The following efficacy endpoints will be evaluated:

- Technical Success: An evaluation of whether the lung nodule was treated according to the study protocol as determined at the immediate post-procedural timepoint. This is in contrast to procedures in which the protocol could not be executed completely, either for technical reasons or for reasons related to comorbid disease.
- Technique Efficacy: An evaluation of whether the lung nodule was effectively ablated. Evaluates whether complete ablation of the nodule was achieved as evidenced by imaging follow-up 1-month post-procedure (including a window of 20-40 days post-procedure).

Full procedures for study visits and the index ablation procedure are described in the section "Assessment of Safety" below.

#### 9.8. Assessment of Safety

#### 9.8.1. Screening / Baseline Visit

A screening/baseline visit will be performed within 30 days prior to the ablation procedure to assess eligibility. The following assessments will be performed and the results recorded on the appropriate subject eCRFs:

- Verification of eligibility criteria
- Subject demographics (e.g.,. subject age, sex, ethnicity, race)
- Subject medical history (e.g., COPD, asthma, emphysema, tobacco history, cancer diagnosis)
- History of prior invasive lung procedures
- Medication use (e.g., immunotherapy, chemotherapy, targeted antineoplastic therapy, prescription antithrombotics)
- Pulmonary function testing (if available per standard of care)
- Quality of Life Survey (EQ-5D)

#### 9.8.2. Baseline Imaging

In accordance with inclusion criteria, nodules  $\leq$  30mm in maximum diameter with  $\geq$  5mm of nodule-free lung parenchyma between target nodule and pleura or fissure are eligible to be considered target nodules for the study analysis. This will be based on standard-of-care (SOC) baseline imaging.

One target nodule per subject will be identified on a SOC baseline CT prior to patient consent. If the study subject has more than one nodule meeting the above criteria, the most easily accessible nodule, as determined by the physician investigator, will be targeted for the study.

MDT18010ILSBA

Version 4.0

26-SEP-2019

Page 26 of 50

